5.5 Toxicities to be monitored

Monitoring for side effects from anastrozole will be done per their standard of care by patient's treating physician.

5.6 Follow Up

Patients will not be followed for this study after completion of the 6 mths blood draw, study questionnaires. However, they will continue to follow-up with their treating physician per standard of care.

6. Criteria for Evaluation

The primary endpoint is comparing baseline oxylipin levels for patients who develop AIMSS vs. those who do not develop AIMSS. For this pilot trial of 20 evaluable patients we expect 10 patients to develop AIMSS and 10 who do not develop AIMSS. The goal is to prospectively evaluate for any baseline levels in both groups and for changes in oxylipin panels.

7. Statistical Considerations:

This is a pilot study to estimate the values needed to design a larger study. The primary objectives are to estimate the baseline oxylipin levels in patients who develop AIMSS vs. those who do not develop AIMSS. Descriptive statistics and 95% confidence intervals will be computed for two baseline oxylipin levels (PGE₂ and 12-HETE) for each group. Based on clinical observation, it is expected that 50% of the women will develop AIMSS. Ten patients in each group will allow us to estimate the 95% confidence interval with width 1.4 times the observed standard deviation. Although we will not formally test for differences between the two groups, we will estimate the difference between the means with a 95% confidence interval, to inform the sample size justification for a larger study.

The secondary objectives are to correlate changes in oxylipin levels with changes in pain scores. These analyses will be based on all 20 women, irrespective of whether they develop AIMSS. We expect that only a small number of women may switch to another AI due to the development of AIMSS. For these women, we will use the values obtained at the time of the switch. Linear regression will be used to estimate the change in pain scores (as measured by the BCPT-MS) versus changes in PGE₂, 12-HETE. Additionally, we will control for changes in depression levels as measured by the PHQ-9. This model will allow us to estimate the effects of each of the oxylipin measures adjusted for depression in a single model.

8. Data and Safety Monitoring Plan

The University of Arizona Cancer Center Data and Safety Monitoring Board (DSMB) has determined that this study falls into the low risk category with regards to DSMB oversight or QA/QC Program monitoring, per the current University of Arizona Cancer Center Data and Safety Monitoring Board (DSMB) Charter

This trial will undergo monitoring as indicated below:

Identification of the DSMB obligated for oversight responsibilities:

The University of Arizona Cancer Center Data and Safety Monitoring Board (DSMB) will provide ongoing oversight for this trial. This study has been assigned a Low Risk level by the DSMB.

Identification of the entity obligated for routine monitoring duties:

Routine monitoring will be provided by the Quality Assurance/Quality Control (QA/QC) Program to ensure that the investigation is conducted according to protocol design and regulatory requirements.

This trial will also undergo real-time monitoring by the PI and study team, including documentation of real-time monitoring of any new or ongoing safety issues. PI will review with the study team on a monthly basis regarding any routine safety or adverse issues. Adverse events and serious adverse events will be dealt right away as per DSMB/IRB requirements. The study team will inform the PI via email regarding any AE's and subsequent notification forms for the AE's will be completed and filed.

Monitoring progress and data review process:

Routine monitoring of subject data will be conducted at least quarterly.

The first routine monitoring visit will include at a minimum:

- Informed consent – 50% of cases enrolled;
- Subject eligibility – 10% of cases, up to two subjects;
- Data review – 10% of cases, up to two subjects.

All subsequent monitoring visits will consist of randomly selected subject cases based on current enrollment and include continuing review of previously selected cases, as applicable.

A monitoring visit report and follow-up letter will be completed approximately two weeks after the routine monitoring visit; a copy will be maintained in the study file. The monitor will request additional source documentation, clarification, information, or corrections to the CRF and/or regulatory records from the Clinical Research Coordinator (CRC) or other applicable staff responsible for the study and resolution of queries/findings. Documentation of such a request will be maintained with a copy of the monitor's visit report for follow-up at the next monitoring visit. Electronic records will be available in the institutional database or provided by the QA/QC Program staff.

The Principal Investigator will ensure the accuracy, completeness, legibility and timeliness of the data reported in the Case Report Form (CRF), or other acceptable data formats. Source documentation supporting the study data should indicate the subject's participation in the trial and should document the dates and details of study procedures, adverse events, and patient status.

Case report forms, which include the inclusion/exclusion criteria form, adverse event forms and serious adverse event forms, etc. should be completed via the institution database or other acceptable data formats. Trials using paper CRFs will have the data entered with a black ball-point pen or typed. Corrections to the forms should not obscure the original entry and should be made by striking the incorrect information with a single line. Each strike should be accompanied by the initials of the corrector and the correction date. All subject forms and study files will be stored in a secure area limited to authorized staff.

Note: Routine monitoring of regulatory documents will be conducted at least annually.

Process to implement study closure when significant risks or benefits are identified:

This study may be prematurely terminated, if in the opinion of the principal investigator there is sufficient reasonable cause.

Circumstances that may warrant termination include, but are not limited to:

- * Determination of unexpected, significant, or unacceptable risk to patients
- * Failure to enter patients at an acceptable rate
- * Insufficient adherence to protocol requirements
- * Insufficient complete and/or evaluable data

Description of adverse events and reporting procedures:

This study evaluates changes in oxylipins when patients with breast cancer are treated with anastrozole. Side effects from anastrozole will be managed per standard of care and will not be captured as adverse events for the purpose of this study. Since the other study procedures are blood draws and questionnaires, we do not anticipate to have AE or SAEs.

Plan for assuring data accuracy and protocol compliance:

Routine study activity and safety information will be reported to the DSMB on a quarterly basis, or more frequently if requested. These reports will include:

- Study activity, cumulative and for the period under review;
- Safety (narrative description on non-serious and serious adverse events, protocol pre-determined early stopping rules for safety or treatment-emergent adverse events);
- Predetermined protocol early stopping rules for efficacy/futility;
- Status of study in relationship to stopping rules;
- Current dose level of study agent;
- Routine monitoring and protocol compliance (describe the monitoring process and identify the status of the monitoring);
- Comments;
- Attachments (AE data reviewed by the PI to compile the report, SAE letters and reports, results of any review(s), applicable correspondence with the IRB or other regulatory agencies

Data, safety and study progress will be reported to:

- Human Subjects Protection Program (IRB) at least annually;
- Sponsor (if applicable) at least annually.

Identification of the sponsor or funding agency, as applicable:

The PI will immediately notify, in writing, the funding agency, if applicable, any action resulting in a temporary or permanent suspension of the study.

A copy of this correspondence will also be forwarded to the DSMB and the SRC.

9. Data Submission Schedule

Data forms must be completed for all subjects registered to the study. Electronic case report forms will be completed in the OnCore system.

10. Ethics

The trial will be conducted in accordance with the Declaration of Helsinki for biomedical research involving human subjects and local regulatory requirements.

Ethical Principles

This study will be conducted in accordance with Title 21 of the Code of Federal Regulations (CFR). Specifically, this study will be conducted under a protocol reviewed by an Institutional Review Board; the study is to be conducted by scientifically and medically qualified persons; the benefits of the study are in proportion to the risks; the rights and welfare of the patients will be respected; the physicians conducting the study will ensure that the hazards do not outweigh the potential benefits; the results to be reported will be accurate; patients will give their informed consent and will be competent to do so and not under duress; and the study will comply with the ethical principles in Title 21 of the CFR.

Informed Consent

This study will be conducted in full compliance with the informed consent regulations in 21 CFR 50. The Sponsor-Investigator is responsible for ensuring that written informed consent from potential patients is obtained prior to performing any trial tests or assessments required by the protocol.

A copy of the fully executed informed consent form (PHI authorization form and ancillary consent forms if applicable), is given to the subject. One copy is placed in the subject's medical record, another copy is placed in the research chart, and the originals are filed by the protocol number in room 2111 at UACC North Campus.

Institutional Review Board

This study will be conducted in full compliance with the Institutional Review Board (IRB) regulations in 21 CFR 56, in accordance with the Declaration of Helsinki. This protocol will not be initiated unless it and the informed consent form have been reviewed and approved by, and remains open to continuing review by, an IRB meeting the requirements of 21 CFR 56. The IRB shall review and have the authority to approve, require modification in (to secure approval), or disapprove the protocol. The IRB shall notify the Investigator and the institution in writing of its decision. The IRB shall require that the information given to patients as part of the informed consent is in accordance with 21 CFR 50.25. The IRB shall conduct continuing reviews of the protocol at intervals appropriate to the degree of risk, but not less than once per year. At the completion or early termination of the trial, a final report should be sent to the IRB by the Investigator. The Investigator is obligated to maintain an IRB correspondence file.

Confidentiality of Patient Data

The investigator must ensure that patient confidentiality will be maintained. Patients will be identified by initials and a protocol-assigned patient number as described in section 4.5. Permission for direct access to patient data will be sought in writing for the patient by the investigator as part of the informed consent procedure. The patient will be informed

that all clinical information is confidential, but that the IRB, and regulatory authorities may inspect these records.

11. Bibliography

1. Ker RF. Dynamic tensile properties of the plantaris tendon of sheep (*Ovis aries*). *J Exp Biol.* 1981;93:283-302.
2. Burstein HJ. Aromatase inhibitor-associated arthralgia syndrome. *Breast.* 2007;16(3):223-234.

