Feasibility Issues: From 2015 to 2016, ~40 patients were started on adjuvant anastrozole therapy who meet our eligibility criteria. Thus, we anticipate accrual of 2-3 patients per month and completion of accrual this pilot study within 8-12 months of study initiation. Based on previously published studies, it is expected that 50% of women initiating AI will develop AIMSS within one year, with most women experiencing symptoms by 2 months.¹⁷ Women who discontinue use of anastrozole before the 6 month visit will complete all measurements at the time that they switch to another AI and come off study.

[name] and the research personnel will be conducting monthly meetings to review patient accrual data, address any barriers to accruals and resolve them in a timely manner. [name] will be overseeing the oxylipin data analysis.

STUDY CALENDAR

			Treatment -Anastrozole	
	Screening	Pre-Treatment	3mths	6mths
Informed Consent	X ^a			
History and Physical Exam	X ^a			
Collection of Blood for biomarker analysis		X ^{b,d}	X ^{c,d}	X ^{c,d}
Questionnaires		X ^b	X ^c	X ^c

- A- Performed within 28 days of trial entry
- B- May be collected/Performed any time prior to starting anastrozole (can be on the same day)
- C- Can be done within 28 day window (\pm) of the time point
- D- Labs have to be fasting

TABLE OF CONTENTS

	Page
Protocol Synopsis	2
1. Introduction	6
2. Study Objectives	10
3. Study Design	10
4. Selection of Patients	10

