Adjuvant aromatase inhibitor (AI) therapy is the recommended first-line adjuvant treatment for postmenopausal women with estrogen receptor positive (ER+) breast cancer based on improved disease-free survival (DFS) compared to tamoxifen in randomized control trials. More recently extended adjuvant AI therapy (for 10 years) has been shown to improve DFS when compared to placebo in women who completed 5 years of standard AI therapy.^{1,2} However, AI therapy has been associated with significant, activity-limiting musculoskeletal symptoms including arthralgia, myalgia and joint stiffness or AI-induced musculoskeletal syndrome (AIMSS).³ AIs block estrogen synthesis and induce menopausal symptoms that are particularly severe in younger patients.^{4,5} Musculoskeletal complaints are among the most commonly reported and debilitating side effects of adjuvant AI therapy;⁶ findings that are supported by observations in aromatase knockout mice which exhibit increased pain responses.⁷ Among women with arthralgia syndromes at initiation of AI therapy, half report symptom exacerbation. Joint-related symptoms manifest early after initiation of AI therapy with worsening of symptoms up to 1 year post-initiation of AI.^{8,9} AIMSS impairs ability to perform activities of daily living as well as work-related tasks as the most commonly affected joints are hands, knees and hips.^{10,11} In a survey conducted by Breast Cancer Action, 27% of respondents reported that they had discontinued adjuvant AI use because of adverse effects (AE), with AIMSS being the leading AE.¹² In a cohort study in California, 61% of patients on AIs developed joint and/or bone pain resulting in discontinuation of therapy in 20% of patients.¹³ In a recent study, full adherence, defined as full duration and optimal schedule, was observed for only 49% of breast cancer (BC) patients prescribed any hormone therapy (HT) and was related to higher mortality in those who discontinued [Hazards Ratio (HR) = 1.26 (Confidence interval (CI) 1.09–1.46)] or were non-adherent to HT [HR = 1.49 (CI 1.23–1.81)].¹⁴ This study is concerning and consistent with clinical trial evidence from prior tamoxifen studies showing higher recurrence rates and worse outcomes with < 5 years or suboptimal HT use.^{15–17} Clearly, there is a need to maximize efficacy and improve tolerance to AIs. Approaches to study interventions that enhance both adherence and response rates for AIs are important research and clinical gaps that must be addressed to reduce death from breast cancer.^{18,19} **A critical first step is to identify those who are at risk of developing AIMSS by developing predictive biomarkers that will provide physicians opportunity for early intervention, thereby improving adherence to AIs. Currently there are no predictive biomarkers available to identify those at risk of developing AIMSS.**

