5.4 Self-reported questionnaires

The following questionnaires will be administered for the study to look for potential confounders like depression which can influence reporting of pain. The pain questionnaires will help us classify AIMSS in an objective way.

Pain Assessment. Breast Cancer Prevention Trial–Musculoskeletal Symptom (BCPT-MS) subscale and The Western Ontario and McMaster Osteoarthritis Index (WOMAC) have been validated as the most responsive tools for evaluating the development of AIMSS.⁶² These tools will be administered by the study nurse.

BCPT-MS: Individuals with a subscale score of ≥ 1.5 on the BCPT-MS are considered to have developed AIMSS, and it is expected that 50% of our sample will develop AIMSS.^{62,63} Our primary study endpoints will be correlated to three items on the BCPT-MS: general aches and pains, joint pain, and muscle stiffness.^{64,65} The BCPT-MS was derived from the original BCPT Symptom Check-list, a 18-item questionnaire validated in breast cancer survivors.⁶⁶ The subscale score consists of the mean of responses to three questions addressing general aches and pains, joint pain, and muscle stiffness(questions 8,9,10 of the attached subscale). Scores range from 0–4, with higher scores representing worse symptoms. Changes in the BCPT-MS subscale have been shown to be the most responsive to changes in AIMSS with 54% of women developing AIMSS within 6 months.⁶²

WOMAC: The WOMAC is a 24-item instrument developed to assess pain, stiffness, and physical function in participants with hip and/or knee osteoarthritis.⁶⁸ This instrument is well validated and has been modified from its original form, and used extensively to examine specific joint pain changes following treatment, including drug-based (NSAID) interventions for back pain, rheumatoid arthritis, and fibromyalgia.⁶⁹⁻⁷⁸ For our study, we will use the 5-point Likert format.

Depression Questionnaire. It has been reported that up to 50% of newly diagnosed breast cancer patients have symptoms of depression or anxiety⁷⁹ and perception of pain may be altered in individuals with symptoms of depression.⁸⁰ Therefore, we will also administer the Patient Health Questionnaire (PHQ)-9 questionnaire, which is a validated multipurpose tool used for screening, diagnosing, monitoring, and measuring severity of depression.⁸¹ Additionally, the PHQ-9 has been successfully used in breast cancer patients to evaluate psychometric properties.^{82,83}

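### The secondary regression of BCPT-MS change omits the baseline BCPT-MS score; a baseline-adjusted fit should be prespecified and reported beside it

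*Combined protocol and SAP*

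**What the plan says.** Section 7 (Statistical Considerations) defines the secondary analysis: "Linear regression will be used to estimate the change in pain scores (as measured by the BCPT-MS) versus changes in" PGE2 and 12-HETE. It then adds one adjustment: "Additionally, we will control for changes in depression levels as measured by the PHQ-9". Everything goes into one fit: "This model will allow us to estimate the effects of each of the oxylipin measures adjusted for depression in a single model". The sample is fixed as well: "These analyses will be based on all 20 women, irrespective of whether they develop AIMSS". No section adds baseline BCPT-MS, or any other baseline value, to this model.

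The baseline score will be available. The study calendar in the synopsis schedules the questionnaires before treatment, as well as at 3 and 6 months. Section 5.4 describes the BCPT-MS subscale as the mean of three items: "Scores range from 0–4, with higher scores representing worse symptoms". The eligibility criteria in sections 4.1 and 4.2 exclude autoimmune arthritis and daily NSAID use other than aspirin, but set no limit on the entry score. The Introduction recognises that some women start with symptoms: "Among women with arthralgia syndromes at initiation of AI therapy, half report symptom exacerbation".

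**The concern.** On a bounded scale, change is constrained by the starting value. A woman at 0 cannot fall, and a woman at 3 can rise by at most 1. Imperfect visit-to-visit correlation adds ordinary regression to the mean. A model of change that omits the baseline score leaves any such dependence in the error term.

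Two things could follow. First, the oxylipin slopes, which are the plan's answer to the secondary objective and rest on 20 women, may have wider intervals than the collected data permit. Second, if women with more pain at entry also have different oxylipin levels at entry, both variables regress together. Part of the change-change association would then be an artefact. Because the pilot is meant to supply values for designing a larger study, a slope wrong in size or precision could be carried forward.

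**Working it through.** **The plan's own precision figure.** Section 7 gives one, for the primary objective: "Ten patients in each group will allow us to estimate the 95% confidence interval with width 1.4 times the observed standard deviation". The check is 2 × t(0.975, 9)/√10 = 2 × 2.262/3.162 = 1.43 SD, which agrees. No precision is stated for the regression slopes.

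**Inputs.** From section 7: n = 20 and three predictors plus an intercept, so 16 residual degrees of freedom as planned and 15 with the baseline added. From section 5.4: a score from 0 to 4. Assumed, because the documents do not give them: the baseline/follow-up correlation ρ, and q, the ratio of baseline SD to follow-up SD.

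**Precision when oxylipin change is unrelated to baseline pain.** In units of follow-up variance, Var(change) = 1 + q² − 2ρq, and Var(change given baseline) = 1 − ρ². With q = 1 the ratio is (1 − ρ²)/(2 − 2ρ) = (1 + ρ)/2, that is 0.65, 0.75 and 0.85 at ρ = 0.3, 0.5 and 0.7.

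The extra predictor costs √(15/14) = 1.035 in standard error (normal predictors) and 2.131/2.120 = 1.005 in the t quantile, together 1.041. At ρ = 0.5 the interval-width ratio is √0.75 × 1.041 = 0.90. Break-even is at (1 + ρ)/2 = 1/1.041² = 0.923, so ρ is about 0.85.

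The table gives interval width with the baseline added, relative to the planned model:

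| Setting | ρ = 0.3 | ρ = 0.5 | ρ = 0.7 | ρ = 0.9 |
|---|---|---|---|---|
| q = 0.6 | 0.99 | 1.03 | 1.03 | 0.86 |
| q = 0.8 | 0.92 | 0.98 | 1.03 | 1.01 |
| q = 1.0 | 0.84 | 0.90 | 0.96 | 1.01 |
| q = 1.2 | 0.76 | 0.81 | 0.85 | 0.86 |
| Simulated bounded score | 0.87 | 0.93 | 0.99 | 1.03 |

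The last row uses 4,000 simulated trials of 20 women per setting. Scores were rounded to thirds and cut off at 0 and 4, with underlying means of 0.9 at baseline and 1.5 at follow-up and SD 0.9 at both. Repeat runs move these ratios by about a point.

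**Regression to the mean when baseline oxylipin and baseline pain are related.** Let their baseline correlation be c, let the visit-to-visit correlations be a (oxylipin) and b (pain), and let there be no other link. With unit SDs, Cov(change, change) = c(1 − a)(1 − b). For a = b = 0.5 both change variances equal 2(1 − 0.5) = 1, so the spurious correlation is 0.25c. Taking c = 0.66 purely as an illustration gives 0.25 × 0.66 = 0.165. Conditioning on an error-free baseline pain score gives 0.

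On a simulated bounded score with c = 0.66 and a true slope of zero, the planned slope averaged about 0.15 to 0.17 at ρ = 0.3 and 0.10 at ρ = 0.5. The adjusted slope averaged about −0.02 and −0.03. Root mean squared error fell from 0.301 to 0.242 and from 0.252 to 0.229.

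**Oxylipin change itself correlated 0.5 with baseline pain.** The adjusted interval was then wider, by a factor of 1.02 to 1.17 over ρ = 0.3 to 0.9. The unadjusted slope averaged 0.02, 0.10 and 0.18 at ρ = 0.3, 0.5 and 0.7, against 0.29 adjusted. This simulation defines the true effect conditional on the starting score, which favours the adjusted model by construction.

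**The case against.** The strongest reply is that the planned model does what the objective asks, which is to relate change to change. Oxylipin change is observed, not randomised, so adding the baseline alters the quantity estimated. It can also introduce bias when the baseline score contains measurement error. In a simulation with true pain change independent of oxylipin change, oxylipin change correlated −0.3 with true baseline pain, and score reliability of 0.5 to 0.7 (all assumed), the planned slope was 0.00 and the adjusted slope was −0.16 to −0.10. This stands. It is why the adjusted model should be reported with the planned one and not treated as the correct answer.

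The precision gain is also conditional. Half the women are expected to reach a score of 1.5 or more on treatment, which could spread the follow-up scores and make q less than 1. The gain then shrinks or reverses, as the table shows. The two harms also pull apart: the full gain needs oxylipin change unrelated to baseline pain, whereas the bias needs the baseline values to be related. This stands too.

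A reader might infer three stronger things that the documents do not support:

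- **That baseline BCPT-MS is the strongest known predictor of change.** Nothing in the protocol says so. The Introduction's figure of half worsening among women with arthralgia at the start does not show dependence on the starting score, since about half of all women are expected to develop AIMSS.
- **That the preliminary data demonstrate the bias.** The value 0.66 is the square root of the R² of 0.44 for 12-HETE in Table 2. That is the largest of seven listed values, from 10 women already stable on AI and a different pain item. Section 1 itself says those samples have no true baseline.
- **That adjustment removes the floor and ceiling problem.** A linear covariate does not.

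What the objection does not remove is that a collected, plausible predictor of the outcome is left out with no reason given.

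**Conclusion.** The point holds in conditional form. The omission is certain from section 7, and the availability of the baseline score is certain from the study calendar. That change depends on the starting score is likely, given the bounded scale and unrestricted entry score, but the documents do not show it.

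The planned slopes are therefore likely, not certain, to be less precise than they could be at low to moderate correlation. With equal SDs and ρ from 0.3 to 0.7 the loss is modest. It is absent or slightly reversed near ρ = 0.9, or at ρ = 0.7 with q = 0.8. Regression-to-the-mean bias is possible if baseline oxylipins and baseline pain are related, but its size cannot be fixed from the documents. It does not follow that the planned model is invalid or that the adjusted one is guaranteed to be unbiased.

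Severity is low to moderate: this is a secondary, estimation-only analysis in a pilot, and the primary comparison is unaffected.

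**What to change.** In section 7, prespecify a second model that adds baseline BCPT-MS as a covariate to the regression of BCPT-MS change on changes in PGE2, 12-HETE and PHQ-9. Modelling the follow-up score with the same covariates gives identical oxylipin slopes. Report it beside the planned unadjusted model, with 95% intervals from both. State in advance that any disagreement will be read with caution, because the oxylipin changes are observed and the baseline score is measured with error.

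Reporting the baseline/follow-up correlation and both SDs would also give the larger study the inputs missing here. The cost is a sentence or two in section 7, one extra fit, and one of 16 residual degrees of freedom in that fit. No new data are needed. Prespecifying both fits also prevents a choice between them after the results from 20 women are known.

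### Section 7 describes only a PHQ-9-change-adjusted secondary model; because PHQ-9 change may be a cause or a result of pain change, the oxylipin slopes should be reported with and without it

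*Combined protocol and SAP*

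**What the plan says.** The secondary objective, in the synopsis and in Section 2, is to correlate changes in oxylipin levels with changes in pain scores. Neither place mentions conditioning on mood.

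Section 7 (Statistical Considerations) turns this into a regression: "Linear regression will be used to estimate the change in pain scores (as measured by the BCPT-MS) versus changes in" PGE2 and 12-HETE. The sample is fixed: "These analyses will be based on all 20 women, irrespective of whether they develop AIMSS". Section 7 then adds the covariate, "Additionally, we will control for changes in depression levels as measured by the PHQ-9", and describes the product: "This model will allow us to estimate the effects of each of the oxylipin measures adjusted for depression in a single model". It names no model without PHQ-9 change and no sensitivity analysis.

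The reason for collecting PHQ-9 is in Section 5.4, where the questionnaires are given "to look for potential confounders like depression which can influence reporting of pain", on the ground that "perception of pain may be altered in individuals with symptoms of depression".

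The Study Calendar puts all questionnaires at the same three visits: pre-treatment, 3 months and 6 months. Section 7 does not say whether change runs to month 3 or month 6. The shared visits nevertheless make pain change and PHQ-9 change concurrent.

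**The concern.** Section 5.4 treats depression as something that acts on pain reports. The covariate in Section 7 is change in depression during treatment, and that could also be a result of new pain. The Introduction says that "AIMSS impairs ability to perform activities of daily living as well as work-related tasks". The synopsis (Feasibility Issues) expects most women to have symptoms by 2 months, which is no later than about the time of the first on-treatment questionnaire. That lower mood follows is an inference and is not stated in the documents, but the plan neither excludes it nor mentions it.

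Conditioning on a consequence of the outcome distorts the slope of the exposure. In the simplest case it pulls the slope toward zero. The study is a pilot meant to supply values for a larger one, and the secondary slopes would be carried forward without any sign of how far they depend on the assumed direction.

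**Working it through.** **The plan's own figure.** Section 7 gives one precision figure, for the primary objective: a 95% interval 1.4 SD wide with 10 women per group. Check: 2 × t(0.975, 9 df) / √10 = 2 × 2.262 / 3.162 = 1.43. It reproduces and is not affected by this point. Section 7 gives no figure for the secondary regression.

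**Inputs.** The model form and n = 20 come from Section 7. The documents give neither the correlation between PHQ-9 change and pain change nor the slope for changes, so both are assumed and shown over a range. Write X for oxylipin change, Y for pain change and D for PHQ-9 change. X and Y are standardised and the true slope is b = 0.5.

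**Case 1: pain change drives PHQ-9 change.** Y = bX + e with var(e) = 1 − 0.25 = 0.75, and D = cY + u. The coefficient of X given D is b × var(u) / (var(u) + c² var(e)). Scaling D to unit variance gives c = r and var(u) = 1 − r², where r is the correlation of Y and D.

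| r | Factor | Adjusted slope | Attenuation |
|---|---|---|---|
| 0.3 | 0.91 / (0.91 + 0.0675) = 0.93 | 0.47 | 7% |
| 0.5 | 0.75 / (0.75 + 0.1875) = 0.80 | 0.40 | 20% |
| 0.6 | 0.64 / (0.64 + 0.27) = 0.70 | 0.35 | 30% |

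**Case 2: mood change is a true confounder.** Assume mood change correlates 0.4 with oxylipin change and has a standardised effect of 0.4 on pain change. The slope without D is 0.5 + 0.4 × 0.4 = 0.66, which is 32% too high. The slope with D is 0.50.

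**Case 3: both directions operate.** Let M be exogenous mood change with unit variance and correlation −0.3 with X. Let Y = 0.5X + 0.4M + e with var(e) = 0.75, and D = M + 0.4Y.

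- Without D, the slope is 0.5 − 0.4 × 0.3 = 0.38.
- Given X, var(M) = 1 − 0.09 = 0.91.
- Given X, cov(Y, D) = 0.4 × 1.16 × 0.91 + 0.4 × 0.75 = 0.722.
- Given X, var(D) = 1.16² × 0.91 + 0.16 × 0.75 = 1.345. The coefficient of D is therefore 0.722 / 1.345 = 0.537.
- The slope of D on X is −0.3 + 0.4 × 0.38 = −0.148.
- With D, the slope is 0.38 + 0.537 × 0.148 = 0.46.

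Both slopes lie below the true 0.50.

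**Check at the planned size.** A simulation with n = 20, both oxylipin terms and 3,000 runs per setting used a standardised slope of √0.44 = 0.663. The 0.44 is the 12-HETE R² in Table 2; it is cross-sectional, from 10 women and a different pain item, so it only sets the scale. Here r is the correlation of Y and D given X, for which the Case 1 factor is 1 − r².

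| Assumed direction | Slope without D (r = 0.3 / 0.5 / 0.7) | Slope with D |
|---|---|---|
| Pain drives PHQ-9 | 0.67 / 0.67 / 0.66 | 0.61 / 0.50 / 0.34 |
| Depression drives pain, unrelated to oxylipins | 0.66 / 0.67 / 0.66 | 0.66 / 0.66 / 0.66 |
| Confounder (correlation 0.4 with oxylipin change) | 0.75 / 0.82 / 0.88 | 0.66 / 0.67 / 0.66 |

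In the second row at r = 0.5, adjustment also narrows the 95% interval from 0.77 to 0.69.

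**The case against.** The strongest reply is that the only direction the documents state is depression acting on pain reports. Under that direction the planned adjustment is harmless, gains precision or removes confounding. Regressing change on change, with change in a time-varying confounder as a covariate, is a coherent specification. This stands: it rules out simply removing PHQ-9 change or treating the slope without it as the correct one. Replacing it with baseline PHQ-9 is no clear improvement either. A stable additive effect of depression already cancels from a change score, and mood change during treatment would be left uncontrolled.

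It can also be said that Section 7 introduces the adjustment as an addition, which could imply a regression without PHQ-9 first. That reading is possible, but the reference to a single model favours one adjusted fit, and no report of an unadjusted slope is promised.

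Three stronger conclusions are tempting, and the documents support none of them:

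- A reader might infer that the planned slope is certainly too small. No passage says that AIMSS raises PHQ-9, and the net bias can go either way.
- A reader might infer that the two models bracket the truth. Case 3 shows that they need not.
- A reader might infer a loss of power, or that a marker would be dropped. Section 7 sets no test, power target or selection rule for the secondary analysis.

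**Conclusion.** The point holds as one of interpretation and reporting. The single model described conditions on a concurrent post-baseline variable whose causal place the documents leave open, while the objective is the association without that conditioning. If pain drives mood, the attenuation is about 7% to 30% under the assumed correlations of 0.3 to 0.6 and slope of 0.5. If mood change confounds, the adjusted slope is right and the other is biased. All these sizes rest on assumed values. The reply leaves one gap open: with a single adjusted slope, the reader cannot see how far the result depends on the assumption in Section 5.4. The point concerns a secondary estimate in a pilot and leaves the primary comparison untouched.

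**What to change.** In Section 7, pre-specify that the slopes for PGE2 change and 12-HETE change will each be reported with a 95% confidence interval from two models, one without and one with PHQ-9 change. Present the slope without PHQ-9 change as the direct answer to the stated objective. Present the slope with it as the estimate under the confounding assumption of Section 5.4. Add that a material difference between the two will be reported as sensitivity to that assumption, with no claim that they bound the true value.

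The cost is a few sentences and one further regression on data already collected. The downside is two sets of slopes to interpret instead of one.
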